2 STUDY OBJECTIVES

2.1 Primary Objectives

- To evaluate the safety of oral insulin in patients with nonalcoholic steatohepatitis (NASH) and type 2 DM.

2.2 Secondary Objective

- To assess whether oral insulin may be effective in reducing liver fat content and inflammation in patients with NASH and type 2 DM.

3 INVESTIGATIONAL PLAN

3.1 Overall Study Design and Plan

This is an open, multi-center study using the oral ORMD-0801 insulin formulation in patients with NASH and confirmed type 2 DM. This exploratory multi-center study will enroll 40 patients with NASH and type 2 DM between the ages of 18 and 70. Subjects will undergo a screening phase up to 42 days prior to enrolment for 2 weeks, a treatment phase for 12 weeks and an end-of-study phase after completion of 4 weeks, after end of treatment.

At screening (Visit 1, up to week -6), subjects will sign the ICF and inclusion and exclusion criteria will be reviewed. Medical history, demographics (sex, age, race and ethnicity), and prior and concomitant medications will be recorded. Height and weight will be measured, and BMI will be calculated. Vital signs (SBP/DBP, heart rate and oral temperature), complete physical examination, 12-Lead ECG, clinical laboratory evaluations, urine pregnancy test for females of childbearing potential, blood lipids test, HbA1c, viral serology, CAP-Fibroscan and MRI-PDFF will be performed. For females of non-childbearing potential, FSH levels will be tested if results are not available. Adverse events will be monitored and recorded.

After Screening, each subject will undergo a placebo run-in phase (Visit 2, to Week -2). Concomitant medications will be reviewed. All subjects will receive the morning treatment (run in placebo) in clinic, 1 bottle of placebo medication and subject diaries will be dispensed. Vital signs (SBP/DBP, heart rate and oral temperature) and weight will be collected. Fasting blood glucose and fasting insulin will be measured, urine pregnancy test will be performed for females of childbearing potential. Self-monitored fasting morning blood glucose (finger-stick) will be recorded in the patient diaries 3 days weekly in the morning. Adverse events will be monitored and recorded.

Subjects will then undergo a treatment phase consisting of a treatment period of 12 weeks that will start at Visit 3 (Week 0) and outpatient visits at Weeks 1, 2, 4, 8, and 12 (final visit). At each visit, concomitant medication will be reviewed, weight will be measured, ORMD-0801 morning treatment will be administered in clinic, and sufficient quantity of medication will be dispensed to last until the next nominal clinic visit. Medication compliance check will be performed, self-monitored fasting morning blood glucose (finger-stick) will be recorded 3 days weekly in the morning and subjects' diaries will be reviewed. Vital signs (SBP/DBP, heart rate and oral temperature) will be recorded. Adverse events will be monitored and recorded.

At Visit 3, urine and serum pregnancy test will be performed for females of childbearing potential. Additional urine serum pregnancy test will be performed for females of childbearing potential at visits 6, 7 and 8. At Visit 8, subjects will have HbA1c evaluations and MRI-PDFF performed. At Visits 3 and 8, a complete physical exam and fibroscan will be performed.

The end of the study (EOS) Visit (Visit 9) will be conducted 4 weeks following the last scheduled treatment visit. Subjects concomitant medications will be reviewed, and weight will be measured. A complete physical exam and ECG will be performed and vital signs (SBP/DBP, heart rate and oral temperature) will be measured if deemed necessary by the investigator. Clinical laboratory evaluation will be performed. Fasting blood glucose, fasting insulin, HbA1c,

blood lipids and adiponectin levels will be measured. Urine serum pregnancy test will be performed for females of childbearing potential. Subject diaries will be collected and reviewed for self-monitored fasting morning blood glucose. Adverse events will be monitored and recorded. Subjects who are discontinued early from the study will complete the EOS evaluations at the time of early discontinuation.

3.2 Screening/Visit 1 (up to week -6)

Screening process will take place at Visit 1, up to 42 days prior to enrolment. Screening activities will consist of the following:

Visit 1 (up to week -6)

- Informed consent
- Medical history
- Concomitant medication
- Complete Physical examination (PE)
- Weight and height
- ECG
- Vital signs (blood pressure, heart rate, oral temperature). Vital signs will be measured in the sitting position after at least 5 minutes of rest.
- Urine pregnancy test
- Females of non-childbearing potential FSH levels will be tested if results not available.
- Clinical laboratory evaluations
 - Chemistry: Electrolytes, Blood Urea Nitrogen (BUN), international normalized ratio (INR), creatinine, glucose level, liver function tests (LFT) including transaminases (ALT, AST), albumin, and alkaline phosphatases, creatine phosphokinase (CPK), Bilirubin
 - Hematology: Complete blood count (CBC)
 - Thyroid Stimulating Hormone (TSH)
 - HbA1C
 - Blood lipids: Total cholesterol, LDL, HDL, Triglycerides
 - Viral serology: HCV-Ab, HBsAg, HBcore-total, HBs Ab, anti-HIV Ab
- CAP - Fibroscan
- MRI-PDFF
- AE/SAE assessment

For subjects who meet eligibility criteria based on the Screening assessments, instruction will be provided on the following:

- the use of adequate contraceptive methods (see Section 4.1) for the duration of the study (Screening through End of Study (Visit 9);
- minimal use of concomitant medications during the study, if possible, and avoid prohibited medications as defined in Section 5.6;
- maintenance of usual dietary habits and avoidance of drastic changes, such as a conversion to a vegetarian diet;

- restraint from excessive alcohol use or binge drinking during the study, and restraint from drinking alcohol from 72 hours prior to all study visits;
- restraint from excessive caffeine use (i.e., more than five cups of caffeinated beverages per day) during the study.

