5.7 Behavioral Restrictions

Subjects should arrive following a minimum 10-hour fast and must not take any food prior to scheduled dosing as described in the study design. Water intake will be unrestricted. All subjects will continue with their regular diet.

Excessive caffeine use (i.e., more than five cups of caffeinated beverages per day) will not be allowed from Screening through Visit 8. Excessive alcohol use or binge drinking will be discouraged during the study, and alcohol will be prohibited 72 hours prior to each visit. Subjects must refrain from tobacco or nicotine use throughout the study. Subject should not use any recreational or illicit drugs throughout the study.

Subjects will also be asked to refrain from any unusual or unaccustomed vigorous exercise during the course of the study.

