6.4 Efficacy Assessments

Fat content in the liver will be assessed by measuring the final and baseline differences in the MRI and Fibroscan results.

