6.5 Safety Assessments

6.5.1 Weight and Height

Height will be measured, and BMI will be calculated at Screening only with the subject wearing no shoes. Weight will be measured at all visits in fasting conditions when possible (on visits when subject is required to fast). Height will be measured at Screening only with the subject wearing no shoes, coats, jewelry and other accessories.

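### The only pre-treatment MRI-PDFF may be taken under different fasting and alcohol conditions from the Visit 8 scan, and the laboratory and FibroScan baselines do not use the comparable Visit 3 measurements

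*Combined protocol and SAP*

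**What the plan says.** Section 3.2 lists the Visit 1 procedures, which include chemistry (glucose, ALT, AST), CAP-FibroScan and MRI-PDFF. It then continues: "For subjects who meet eligibility criteria based on the Screening assessments, instruction will be provided on the following". One item on the list that follows is "restraint from drinking alcohol from 72 hours prior to all study visits". Section 5.7 repeats the rule without exempting any visit: "alcohol will be prohibited 72 hours prior to each visit".

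Fasting is not on the Section 3.2 list. It appears in Section 5.7: "Subjects should arrive following a minimum 10-hour fast and must not take any food prior to scheduled dosing as described in the study design". Section 6.5.1 implies that not every visit is a fasting visit, because it limits fasting weights with the words "on visits when subject is required to fast". It does not name the visits.

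Section 6.4 defines the imaging measure: "Fat content in the liver will be assessed by measuring the final and baseline differences in the MRI and Fibroscan results". It does not name the baseline visit. Section 8.2.2 calculates laboratory change, and shift tables to Visit 8, from Screening. Section 3.4.1 labels Visit 3 as baseline and repeats chemistry, hematology and lipids there.

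**The concern.** A change from baseline in a single-arm study is only as sound as the match between its two measurements. If the first is taken before patients have been told to abstain from alcohol, and possibly unfasted, while the second falls at a visit covered by both rules, part of the change may reflect preparation for the visit. Section 6.3 reads the difference as effectiveness of ORMD-0801, and there is no concurrent group in which the same shift would appear and cancel. A larger sample would not remove it.

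MRI-PDFF is the most exposed measure. It is the direct measure of liver fat, and no second pre-treatment scan is available. For chemistry and FibroScan a comparable pre-treatment measurement is collected, but the plan either bypasses it or does not say whether it will be used.

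**Working it through.** The plan gives no standard deviation, effect size or shift for any of these measures, so there is no figure of its own to reproduce here. The check sets the sections side by side.

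**1. When the alcohol instruction is given.** Inclusion criteria 4 and 6 (Section 4.1) use MRI-PDFF, CAP and liver stiffness. A patient who meets eligibility on the Screening assessments has therefore already had both scans. Consent is signed at Visit 1 (Section 3.1), and no earlier instruction is described. Followed as written, the sequence gives patients the 72-hour rule too late for the Visit 1 scans, although the rule's wording covers that visit. Exclusion 13 admits women drinking up to 20 g and men up to 30 g a day, so the rule can change behaviour in enrolled patients.

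**2. Whether Visit 1 is fasted.**
- Section 5.7 states the 10-hour fast in the same sentence as scheduled dosing. Visit 1 has no dosing.
- Section 3.2 asks for a glucose level at Visit 1. Fasting glucose and insulin are first named at Visit 2 (Section 3.3.1) and recur at Visits 3, 6, 7 and 8 (Section 3.4.1).
- Section 3.6 states a 10-hour fast expressly for unscheduled visits. Section 3.2 has no such statement for Visit 1.
- At Visit 8, blood is drawn before dosing and a snack follows 30 to 45 minutes after it (Section 5.2.1). Where imaging falls relative to the snack is not stated.

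Visit 1 fasting is therefore unclear. It is neither required in terms nor waived.

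**3. What each measure has available.**

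| Measure | Before treatment | Final | Baseline in the plan | Consequence |
|---|---|---|---|---|
| MRI-PDFF | Visit 1 only | Visit 8 | Visit 1, by necessity | Conditions may differ; no fallback scan |
| FibroScan | Visits 1 and 3 | Visit 8 | Not stated | Comparable scan exists; choice is open |
| Chemistry (ALT, AST, glucose) | Visits 1 and 3 | Visit 8 | Screening (8.2.2) | Comparable sample exists; definition bypasses it |

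Visit 3 blood is drawn before the first active dose (Section 5.2.1). The documents do not say whether the Visit 3 FibroScan also precedes that dose.

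**4. How a shift would enter the result.** Let a fraction p of patients be scanned at Visit 1 under conditions unlike Visit 8, and let those conditions move the reading by δ on average. Then

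expected mean change = drug effect + other changes over time + p × δ.

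The last term does not depend on the sample size. Neither p nor δ is in the documents. The plan does not ask for fasting hours or last alcohol at imaging, so p could not be recovered afterwards.

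**5. Precision and time span.** Assume all 40 patients are evaluable and let s be the SD of change, which the documents do not give. One standard error is s/√40 = 0.158 s, and the 95% interval half-width is 2.023 × 0.158 s = 0.320 s. This interval reflects sampling error only and makes no allowance for p × δ. The Visit 1 to Visit 8 span can reach 42 + 84 = 126 days, against 84 days from Visit 3.

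**The case against.** The strongest reply is that the plan already collects most of what is needed. FibroScan, chemistry and lipids are repeated at Visit 3, after the alcohol instruction and before or at the start of active treatment. That is correct. For those measures the fault lies in the definition of baseline, not in missing data.

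Second, the alcohol wording covers all visits. The opening clause of the fasting sentence in Section 5.7 can be read as general, with only its second clause tied to dosing. The caffeine rule in the same section runs from Screening, so the section is not confined to dosing visits. The non-fasting visits implied by Section 6.5.1 could be Visits 4 and 5, which have no fasting draw. Nor do the documents say that consent and MRI must fall on the same day. All of this stands. It means that different conditions at Visit 1 are possible rather than certain, and that some patients may in fact be fasted and alcohol-free.

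Third, the study is exploratory, is not powered and is analysed descriptively. That lowers the stakes but does not answer the point. Section 8.1 says the sample is meant to show trends in liver fat, and a difference in conditions can create or hide a trend.

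A reader might infer that the mismatch must favour the drug. The documents give no direction or size for the effect of meals or alcohol on any of these measures, and the inference is least secure for MRI-PDFF. A reader might also extend the Section 8.2.2 baseline to triglycerides. That section names hematology, serum chemistry and serology, and the serum chemistry list in Section 6.5.5.1 contains no lipids. Finally, one could count the alcohol-free days that the visit calendar imposes, but such a count describes drinking between visits, not the conditions at a scan.

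**Conclusion.** The point holds in three parts of unequal weight.

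- **MRI-PDFF.** As sequenced, the only pre-treatment scan precedes the alcohol instruction and has no clearly stated fast. Comparability with Visit 8 is left uncontrolled, and the analysis cannot restore it.
- **Chemistry.** Section 8.2.2 conflicts with the Visit 3 baseline label in Section 3.4.1 and passes over samples taken under the Visit 8 rules. Section 6.3 mentions liver function tests alongside MRI, so the choice may affect efficacy as well as safety summaries.
- **FibroScan.** The baseline visit is undefined, although a usable Visit 3 scan exists.

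The size and direction of any bias are unknown. The documents do not support calling the baseline values invalid or the expected change spurious. The conclusion assumes that sites follow the Section 3.2 sequence as written and give no unrecorded instruction before Visit 1. Section 8 defers further detail to a statistical analysis plan. If that detail fixes the baseline for each measure, the second and third parts fall away and the MRI part remains. This is an avoidable weakness that is cheap to correct, not a fatal one.

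**What to change.** - Give the Section 3.2 instructions at consent, and reconcile Sections 3.2, 5.7 and 6.5.1 so that they name the visits at which the fast and the alcohol rule apply.
- State that the protocol's existing 10-hour fast and 72-hour alcohol conditions apply to the baseline MRI-PDFF as at Visit 8. Where consent and scan cannot share a day, schedule the scan later within the 42-day window.
- Record fasting hours and time of last alcohol at each MRI and FibroScan. Flag baseline MRIs taken under other conditions, and report the MRI change with that limitation.
- Define baseline for each measure: Visit 3 for FibroScan and for the laboratory tests taken there, Visit 1 for MRI-PDFF, and Screening for tests not repeated at Visit 3. Amend Section 8.2.2 to match.
- State that the Visit 3 and Visit 8 FibroScans are done at the same point relative to dosing and the snack, and say where the Visit 8 MRI falls in that order.

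The cost is a protocol amendment, two extra items on the case report form and a second screening day for some patients. No test is added.

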3.2.1 Screen Failure

A screen failure is defined as a subject who has signed the ICF, does not meet all the entry criteria outlined in Section 4 of this protocol. Note that this includes assessments through Visit 1 (up to Days -42), prior to receiving IMP.

The Investigator is responsible for keeping a record of all subjects screened for entry into the study and subsequently excluded. The reason(s) for exclusion will be recorded in the source documents and on the Screening log.

Subjects previously screen failed on eligibility criteria, may be re-screened after re-consenting at the discretion of the treating physician.

3.3 Run-in Phase/Visit 2 (to week -2)

The run-in phase will consist of 2 weeks period starting at visit (Visit 2) week -2

3.3.1 Visit 2 (to week -2)

- Concomitant medication
- Weight
- Morning placebo administration (run-in placebo)
- Vital Signs
- Urine pregnancy test
- Fasting blood glucose and fasting Insulin
- Self-monitored fasting morning blood glucose (finger-stick) recorded in the patient diaries 3 days per week in the morning.
- Dispense 1 bottle of Placebo - Patients will take 2 capsules daily of Placebo in the morning, 30 to 45 minutes prior to breakfast and no later than 10 AM for 2 weeks.
- AEs/SAEs assessment

3.4 Treatment Phase (week 0)

The Treatment Phase will consist of a treatment period of 12 weeks that will start at Visit 3 (week 0) and outpatient Visits 3 (baseline) and visits at week 1, 2, 4, 8, and 12 (final visit).

At each visit patients will have:

- Concomitant medication
- Weight
- Morning treatment administration of oral ORMD-0801 insulin formulation
- Medication Compliance check.
- Urine pregnancy test at visit 3 prior to active dosing and at visits 6, 7, 8 and 9.
- Serum pregnancy test at visit 3 prior to active dosing

- Vital signs (blood pressure, heart rate, oral temperature). Vital signs will be measured in the sitting position after at least 5 minutes of rest.
- Self-monitored fasting morning blood glucose (finger-stick) of fasting blood
- AEs/SAEs assessment

3.4.1 Visits 3 (baseline), 6, 7, and 8

- At Visits 3 (baseline), 6, 7, and 8, patients will have:
- Clinical laboratory evaluations (chemistry, hematology)
- Fasting blood glucose and insulin (also used for HOMA estimates)¹
- Adiponectin
- Blood lipids: Total cholesterol, LDL, HDL, Triglycerides

3.4.2 Visits 3 (baseline), 5, 6, 7, and 8

- Return capsules - check compliance
- At visit 3 and 5 - Dispense 1 bottle of ORMD-0801
- At visits 6 and 7 – dispense 2 bottles of ORMD-0801
- Patients will take 2 capsules daily of ORMD-0801 in the morning, 30 to 45 minutes prior to breakfast and no later than 10 AM for 12 weeks.

3.4.3 Visits 3 and 8

At Visits 3 and 8 patients will have:

- Complete PE
- Fibroscan

3.4.4 Visit 8

At visit 8 Patients will have:

- HbA1C
- MRI-PDFF

3.5 End-of-Study (EOS) (Week 16)/Early Discontinuations

The EOS Visit (Visit 9) will be conducted 4 weeks following the last scheduled treatment Visit. Patients will complete the following EOS evaluations:

- Concomitant medication
- Complete PE, only if the investigator deems it necessary.
- Weight
- ECG, only if the investigator deems it necessary.
- Vital signs (blood pressure, heart rate, oral temperature) will be measured in the sitting position after at least 5 minutes of rest, only if the investigator deems it necessary.

¹ HOMA = The Homeostasis Model Assessment

- Clinical laboratory evaluations (chemistry, hematology)
- Fasting blood glucose and fasting Insulin
- Blood lipids: Total cholesterol, LDL, HDL, Triglycerides
- Adiponectin
- HbA1C
- Urine pregnancy test
- AEs/SAEs assessment

Patients who are discontinued early from the study will complete the EOS evaluations at the time of early discontinuation.

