⁸HCV-Ab (hepatitis C virus antibody), HBsAg (surface antigen of the hepatitis B virus), HBcore-total (total hepatitis B core antibody), anti-HIV Ab (human immunodeficiency virus antibody).

⁹Adverse events will be collected throughout the study beginning from the time the patient signs the consent form until the EOS evaluations

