In the event that a subject discontinues the study prior to completion, the date the subject is withdrawn and the reason for discontinuation will be recorded in the source documents and CRF. Although a subject will not be obliged to give his/her reason for withdrawing prematurely, the Investigator will make a reasonable effort to obtain the reason while fully respecting the subject's rights.

All subjects who are randomized and treated (i.e., received any amount of IMP) will be included in the safety analyses. Thus, every effort will be made to contact any subject who fails to attend any follow-up appointments/contacts, in order to ensure that he/she is in satisfactory health. If a subject withdraws from the study as a result of meeting discontinuation criteria after the start of IMP administration, reasonable efforts should be made to have the subject return for the early withdrawal evaluations (Section 3.5). Any subject withdrawn due to a suspected IMP -related AE should be followed until resolution or stabilization of the event.

If a subject becomes pregnant, IMP will be discontinued immediately, and the subject will be referred to an obstetrician/gynecologist experienced in reproductive toxicity for further evaluation and counseling. The subject will be followed until delivery or other termination of pregnancy for outcome.

Subjects may choose to withdraw authorization to use and disclose their PHI. Such withdrawal of authorization must be made to the Investigator in writing. Any PHI collected by the Investigator prior to the date of such withdrawal will continue to be used and disclosed.

The Sponsor has the right to terminate this study, and the Investigator/Investigational Site has the right to close the site, at any time, although this should occur only after consultation between involved parties. The Investigator or representative will notify the IRB in writing of a premature termination of a study or closure of Investigational Site or of a temporary halt of the study, including the reason of such an action and will send a copy of the notification to the Sponsor.

Events that may trigger premature termination of a study or closure of an Investigational Site include, but are not limited to, a new toxicity finding, a request to discontinue the trial from a regulatory authority, non-compliance with the protocol, GCP violations, slow recruitment/low enrollment, or change in development plans for the IMP.

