If either of the criteria listed below is met, enrollment of new subjects and dosing of ongoing subjects will be temporarily stopped. The Investigator, Sponsor, and the Medical Monitor will discuss whether a lower dose or any additional treatment guidelines should be implemented, or if the trial should be permanently stopped. Any proposed changes to the protocol to address such findings will be submitted for review and approval by the IEC/IRB and the Competent Authority prior to re-starting the trial.

1. A death within 30 days after IMP administration where there is a reasonable possibility that the drug caused the event;
2. Two Grade 4 AEs where there is a reasonable possibility that the IMP caused the events.

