7.5 Recording Adverse Events

All adverse events experienced during the trial, regardless of relationship to study medication, must be recorded on the Adverse Event CRF from the time of patient consent until completion of patients End of Study visit (Visit 9). All serious adverse events will be collected through Visit 9. The Investigator must continue to follow all non-serious events possibly related to the study medication and all serious adverse events until they resolve or until the Investigator assesses them in writing as chronic or stable.

Regardless of relationship to study medication, the event must be recorded on the Adverse Event CRF. Adverse event documentation should include the following information:

- Standard medical terminology for the AE
- Description of adverse event
- Date and time of onset
- Date and time of resolution of the adverse event
- Whether or not the event is ongoing
- Severity of the event
- Relationship between the adverse event and the investigational product
- Description of any actions taken (e.g., medications, treatments)
- Outcome of the AE
- Whether or not the effect was serious and/or unanticipated

Whenever possible, a diagnosis should be given when signs and symptoms are due to common etiology (e.g., cough, runny nose, sneezing, sore throat, and head congestion should be reported as "upper respiratory infection"). For the purposes of this study, hypoglycemic events will be considered adverse events and should be recorded in source and CRF records.

When a diagnosis is not available, each adverse event should be reported separately. For example, "nausea and vomiting" should be split into two separate events.

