7.5.2 Reporting of Serious Adverse Events

In accordance with Federal regulations, Investigators will be notified of the occurrence of serious, unexpected and related adverse events.

The Investigator must report all serious adverse events to Sponsor or delegate within 24 hours of the site being notified of the event. Investigators must also report these events to the Institutional Review Board (IRB) in accordance with the IRB's reporting guidelines, within the IRB specified timeframe, or no later than 48 hours after knowledge of the event.

For submission of these events to the Israeli Regulatory Agency- the Sponsor will follow FDA regulations 21 CFR 312.32. If the event is determined to meet the requirements of IND Safety Reporting, then expedited reporting requirements to the FDA will be followed. The Sponsor may need to issue an Investigator notification, to inform all Investigators involved in any study with

the same drug (or therapy) that this serious unexpected suspected adverse reaction (SUSAR) has occurred.

Investigator Reporting Procedures

The PI or other study personnel must immediately (within 24 hours) inform Sponsor or delegate of any AE considered serious (as defined above) or otherwise medically significant. Notification should be via email or facsimile transmission of a written report signed by the PI. Notification must include the PI's assessment as to whether the event was or was not related to the use of the study medication. The Sponsor contact information is as follows:

Oramed Ltd.

[name]

Contact person at Oramed:

[name]

Email: [contact]

[contact]

The Principal Investigator must also promptly inform the governing IRB of the serious adverse event per the governing IRB's requirements.

The CRO will notify Oramed within 24 hours of receipt. Any SAE that occurred within 30 days after last dose will be followed and reported as above.

Pregnancy Reporting

If the subject or partner of a subject participating in the study becomes pregnant during the study or within 30 days of discontinuing study medication, the Investigator should report the pregnancy to Oramed within 24 hours of being notified. The Exposure In Utero form to the Investigator for completion.

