7.9 Assessment of Adverse Event Outcome

Outcome of AEs will be defined according to ICH Topic E2B, ICH Guideline.

- **Recovered/Resolved:** The subject has recovered fully from the AE without any remaining effects or impairment.
- **Recovered/Resolved with Sequelae:** The subject has recovered, but with an after effect possibly due to disease or treatment.
- **Not Recovered/Not Resolved:** The condition is still present.
- **Fatal:** Fatal should only be used when death is possibly related to the AE.
- **Unknown:** The primary outcome is not known at the time of the final assessment. If an outcome for an AE is not available at the time of the initial report, follow-up will proceed until an outcome is known or followed up to the Final Study Visit. Any subject with a possible IMP-related AE at the Final Study Visit will be followed until resolution or stabilization of the event. Further, any SAE, whether or not related to IMP (active or Placebo), that occurs within 30 days following the last dose of IMP will be followed until resolution or stabilization of the event.

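### For treated patients who leave early, no scheduled contact would detect a new SAE, death or pregnancy in the protocol's own 30-day post-dose windows

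*Combined protocol and SAP*

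**What the plan says.** Completers attend the End-of-Study visit (Visit 9) four weeks after the last scheduled treatment visit. For early leavers, Section 3.5 says: "Patients who are discontinued early from the study will complete the EOS evaluations at the time of early discontinuation". Section 3.1 gives the same instruction.

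Two places set the end of collection. Section 7.5 says: "All serious adverse events will be collected through Visit 9". Footnote 9 of Table 1 (Section 3.8) says that adverse "events will be collected throughout the study beginning from the time the patient signs the consent form until the EOS evaluations".

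Four provisions look 30 days past dosing:

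- Section 7.5.2, on SAEs: "Any SAE that occurred within 30 days after last dose will be followed and reported as above".
- Section 7.5.2, on pregnancy: the site reports if the subject or a partner "becomes pregnant during the study or within 30 days of discontinuing study medication".
- Section 7.9, on any SAE, related or not, "that occurs within 30 days following the last dose of IMP will be followed until resolution or stabilization of the event".
- Section 4.3, as one of two criteria for a temporary halt of enrolment and dosing: "A death within 30 days after IMP administration where there is a reasonable possibility that the drug caused the event".

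Section 4.3 also says that "every effort will be made to contact any subject who fails to attend any follow-up appointments/contacts", and it asks for continued follow-up of patients withdrawn for a suspected drug-related event.

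**The concern.** Safety is the primary objective and the primary endpoint. Once the end-of-study evaluations move to the day a patient leaves, the last planned contact may fall on or close to the day of the last dose. The protocol still treats the next 30 days as a period in which SAEs, deaths and pregnancies count, but it plans nothing that would reveal them.

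A new event in that period becomes known only if the patient, a relative or another doctor tells the site. If nobody does, it is missing from the SAE tabulations, and a drug-related death would not reach the halting criterion in Section 4.3. Enrolment is at most 40, so a single missed SAE or death would change the safety summary noticeably.

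**Working it through.** **Inputs.** Visit 8 is at day 84, with a window of 4 days either side (Table 1). Visit 9 is 4 weeks after the last scheduled treatment visit (Section 3.5). The last in-clinic dose is at Visit 8 (Section 5.2.1). The windows are 30 days (Sections 4.3, 7.5.2 and 7.9). The withdrawal rate is not stated.

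**The plan's own calendar.** Week 12 + 4 = week 16, and day 84 + 28 = day 112. This reproduces the week-16 end of study in the title of Section 3.5.

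**Early leavers.** Let t be the days from last dose to the exit visit. Uncovered days = 30 − t. The values of t are illustrations, because the documents give no timing.

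| t (days) | Uncovered days of 30 |
|---|---|
| 0 | 30 |
| 3 | 27 |
| 7 | 23 |
| 14 | 16 |

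**Completers.** 112 − 84 = 28 days covered and 30 − 28 = 2 uncovered. If Visit 9 stayed at day 112 while Visit 8 moved between days 80 and 88, the interval would run from 112 − 80 = 32 days (2 to spare) to 112 − 88 = 24 days (6 uncovered). Section 3.5 ties Visit 9 to the last treatment visit, so this range is only a sensitivity check. The Visit 9 window cannot be read in the copy of Table 1 available.

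**Could another provision reveal a new event after the exit visit?**

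| Provision | What it reaches |
|---|---|
| 4.3, contact after non-attendance | Patients who miss an appointment; a leaver who has done the exit evaluations has none left |
| 4.3, withdrawal for a suspected drug-related event | That event, already known |
| 7.5, continued follow-up | SAEs and possibly related non-serious events already recorded |
| 7.9, follow-up after the final visit | Possibly related events present at that visit, and SAEs within 30 days once known |
| 7.10 | Significant findings present at Visit 9 |
| 3.7, drug stopped under the glucose rules | These patients stay on the visit schedule (under the high-glucose rule, if possible), so they are largely outside the gap |

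Each of these acts on something already known or on a missed appointment. None schedules a contact that asks about new events.

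**What cannot be computed.** With no withdrawal rate and no event rate in the documents, neither the number of leavers nor the number of missed events can be estimated.

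**The case against.** The best defence is that the sections fit together. Section 7.5 describes active collection up to the last visit, and Sections 7.5.2 and 7.9 then impose a duty to report and follow any SAE within 30 days of the last dose. Section 8.2.1 defines a treatment-emergent event by its start and sets no end date, so a late event that is reported is not excluded by definition. This stands, and it limits the point. A reader might infer that SAE responsibility ceases at the exit visit. The documents do not support that: the duty continues, but only passively.

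A reader might also infer that patients withdrawn because of an adverse event are the most exposed. That is not supported either. Anyone withdrawn for a suspected drug-related event must be followed until it resolves or stabilises, and Sections 7.5, 7.9 and 7.10 add follow-up of open SAEs, possibly related events and significant findings. New events may well surface through that contact. The gap is mainly in leavers with nothing open at exit.

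The 30-day windows concern SAEs, pregnancy and death. None covers non-serious events, so they give no ground for collecting those for longer.

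Section 8 defers further detail to the analysis plan. That does not answer the point, because an analysis plan cannot recover events the site never heard about.

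**Conclusion.** The point holds in a narrow form. For treated patients who leave early, scheduled collection stops at the exit visit, and up to 30 days of the protocol's own windows for SAEs, death and pregnancy depend on unsolicited reports. The full 30 days is the worst case, with the exit visit on the day of the last dose. The shortfall falls day for day as the exit visit comes later.

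The number of patients affected is unknown, and no number of missed events is claimed. A reader might extend the criticism to completers. At 28 of 30 days nominally, that is not a material gap.

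The conclusion assumes that the leaver completes the exit evaluations, so that no missed appointment triggers contact, and that the death window in Section 4.3 is counted from the last dose. It is a cheap improvement to ascertainment of the primary endpoint and does not show that the design is unsound.

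**What to change.** 1. Reconcile Section 7.5 and footnote 9 of Table 1 with Sections 4.3, 7.5.2 and 7.9. SAEs, deaths and pregnancies should be collected until the later of two dates: Visit 9 (or the early-discontinuation visit), and 30 days after the last dose. Leave the collection period for non-serious events as it is.
2. In Section 3.5, add one phone contact at or shortly after day 30 post-dose for treated patients who leave the study early. It should ask about SAEs, including death, and about pregnancy. Completers need no extra call.

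The cost is a wording change and one call per early leaver. Some who withdraw may decline the call, so the gap will narrow but may not close completely.
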